## 5.2. Handling of Missing Data

### 5.2.1. Imputation of Laboratory Values

Laboratory data that are continuous in nature, but are less than the lower limit of quantitation or above the upper limit of quantitation will be imputed to the value of the lower or upper limit plus or minus 2 significant digits, respectively (eg, if the results of a continuous laboratory test is < 20 or 2.0, a value of 19.99 or 1.99, respectively, will be assigned in computing summary statistics). KIM-1 values that are reported as below the level of quantitation (<0.112) will deviate from the above rule and be imputed as 0.099.

### 5.2.2. Imputation of Missing Values

Missing laboratory values will be imputed as described in section 5.2.1. Missing dates will be imputed as described in section 5.2.3. If a patient had missing data for any other reason, values will not be imputed.

### 5.2.3. Handling of Incomplete Dates

An incomplete date will occur when the exact date an event occurred or ended cannot be obtained for a patient. Incomplete dates will be imputed as follows:

- For a partial or missing medication date, the medication will be classified as a concomitant medication unless the available part of the date indicates it is impossible for the drug to be concomitant. For example, if only the year for the stop date is available and the year is prior to the year of dosing, the medication will be classified as a prior medication.
- For a partial or missing adverse event (AE) onset date, the event will be classified as treatment-emergent if the month and/or year of the onset date are on or after the initiation of treatment (casimersen or placebo, as appropriate)
- For calculating the time since DMD diagnosis or duration of prior corticosteroid use, if the date of DMD diagnosis or the start date of corticosteroid use has a missing day, but known month and year, then the 15th of the month will be used in the calculation. If the date has a missing day and month and only the year is known, December 31st of the recorded year will be used in the calculation.

In all cases, the original missing or incomplete dates will be presented in the data listings.

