11. ADVERSE EVENTS

11.1. Collection of Adverse Events

All AEs from the time of informed consent through the end of study visit (or early termination from the study) will be recorded in each individual patient's electronic case report form (eCRF). For patients who prematurely discontinue from the study (see Section 8.3), AEs will continue to be recorded until 4 weeks after the last infusion. Over the entire duration of the study, site personnel will ensure that all AEs are recorded appropriately. If an AE occurs, the primary concern is for patient safety and the investigator will use his/her judgment and expertise to determine the appropriate course of action.

If, at any time after the patient has completed participation in the study (see Section 8.3), the Investigator or study staff becomes aware of an SAE that the Investigator believes is possibly/probably or definitely related to the investigational drug product (Section 11.3.1) or is possibly/probably or definitely related to a study procedure (Section 11.3.2), then the event and any known details must be reported promptly to the Sponsor.

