11.4. Recording Adverse Events

All AEs experienced from the time of informed consent/assent to the last follow-up (ie, 4 weeks after the last dose of investigational drug product) will be recorded within each patient's eCRF. Information should include: a concise description of the event; date and time of event onset and resolution; determination of seriousness, severity, corrective treatment, outcome, and relationship to investigational product or study procedure or underlying disease; and any action taken will be recorded. Resolution occurs when the patient has returned to his baseline state of health or further improvement or worsening of the event is not expected.

Whenever possible, a diagnosis will be recorded as an AE, rather than symptoms or isolated laboratory abnormalities related to that diagnosis. Several symptoms or laboratory results that are related to the same diagnosis can thus be part of the same AE.

A medical or surgical procedure is not an AE; rather the condition leading to the procedure should be recorded as the AE. Similarly, death is not an AE, but is rather the outcome of the AE(s) that resulted in death. If the AE(s) leading to death are not known, then death must be reported as an AE. All AEs will be followed until the resolution of AE, completion of the patient's study participation, or study termination, whichever occurs first. Serious AEs will be followed until resolution or until the condition stabilizes or returns to baseline status or until no further follow-up is expected.

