## 5. GENERAL STATISTICAL METHODS AND CONVENTIONS

### 5.1. General Methods

For continuous variables, descriptive statistics will include the number of patients with data to be summarized (n), mean, standard deviation (SD), median, minimum, and maximum.

For categorical/qualitative variables, descriptive statistics will include frequency counts and percentages. The total number of patients in a treatment group will be used as the denominator for percentage calculations, unless stated otherwise.

Unless stated otherwise, summaries of all endpoints will be by treatment group (see below for definitions of treatment groups) for 3 "Analysis Periods" (Double-Blind Period, Casimersen Period and Combined Double-Blind and Open-Label Periods):

Double-Blind Period: Data will include all assessments and events that occurred prior to the first dose of 30 mg/kg of casimersen in the open-label period. The analyses for the double-blind period will be primarily for safety.

Double-blind Period analysis treatment groups are:

- patients who received placebo during the double-blind Period
- patients who received casimersen at 4 mg/kg (Weeks 1-2), 10 mg/kg (Weeks 3-4), 20mg/kg (Weeks 5-6), and 30mg/kg (Weeks 7-8)
- <=20 mg/kg during Week 1 to 6 (only used for select endpoints)
- patients who received casimersen at 30 mg/kg during Weeks 7 to the end of the double-blind period
- patients who received casimersen at any dose level during Weeks 1 to the end of the double-blind period

Casimersen Period: For AEs and other safety-related data analysis, data will include all assessments and events that occurred while patients received casimersen. Assessments and events that occurred in the double-blind period for patients who were on placebo during the double-blind period will be excluded. Assessments and events that occurred during the double-blind period for patients who received casimersen will be included.

Casimersen Period Analysis treatment group is:

- all casimersen treated patients: Patients who receive casimersen in any portion of the study

Combined Double-blind and Open-label Periods: For efficacy data analysis, data will include all assessments and events during both treatment periods of the study.

Combined Double-blind and Open-label Periods Analysis treatment groups are:

- Placebo-Casimersen: Patients who receive placebo in the double-blind period followed by casimersen in the open-label period

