### **Treatment-emergent Adverse Event**

An AE will be considered treatment-emergent if it started, worsened or became serious on or after the start of first infusion.

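### The partial-date rule for AEs in SAP 5.2.3 has no stop-date check, so an event that began and resolved in Screening can be counted as treatment-emergent

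*SAP*

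**What the plan says.** The AE bullet of SAP 5.2.3 (Handling of Incomplete Dates) covers partial or missing onset dates. Its test is that "the event will be classified as treatment-emergent if the month and/or year of the onset date are on or after the initiation of treatment". The start of treatment is glossed as "casimersen or placebo, as appropriate", without saying which applies to which analysis period. The bullet does not mention a stop date.

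The medication bullet just above it works differently. It defaults to concomitant "unless the available part of the date indicates it is impossible for the drug to be concomitant", and its example uses a stop date: "if only the year for the stop date is available and the year is prior to the year of dosing".

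Four other provisions bear on the point:

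- SAP 5.8, definition of a TEAE: "An AE will be considered treatment-emergent if it started, worsened or became serious on or after the start of first infusion".
- Protocol 11.1, collection: "All AEs from the time of informed consent through the end of study visit" are to be recorded.
- Protocol 11.4, information recorded for each AE: it includes "date and time of event onset and resolution".
- SAP 5.1, Casimersen Period: "Assessments and events that occurred in the double-blind period for patients who were on placebo during the double-blind period will be excluded".

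**The concern.** The rule in SAP 5.2.3 and the definition in SAP 5.8 can give opposite answers for the same event, and the recorded data may already settle which is right. An AE that ended before the first infusion cannot have started, worsened or become serious on or after it. If only its onset month is known and that is the month of first dosing, SAP 5.2.3 nevertheless makes it treatment-emergent.

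AE incidence is the first component of the primary endpoint (Protocol 7.3), and SAP 4.4.1 implements it as TEAE incidence. SAP 6.8.1 in general tabulates only TEAEs, so this classification decides whether an event enters a table or appears only in a listing. With 8 casimersen and 4 placebo patients in the double-blind period, one event is visible.

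**Working it through.** The plan states no figure on this point, so there is nothing to reproduce. The check applies the rule to worked cases and then sizes the effect.

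**Can the situation arise?** AEs are recorded from consent (Protocol 11.1). Screening lasts up to about 4 weeks (Protocol synopsis). Resolution dates are collected (Protocol 11.4). The Double-Blind Period in SAP 5.1 takes in everything before the first open-label 30 mg/kg dose and sets no lower limit at Day 1. The period filter therefore does not remove a Screening event, and only the treatment-emergent flag can.

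**The rule as written.** Treatment-emergent if the onset year is later than the start year, or if the years are equal and the onset month is either unknown or not earlier than the start month. **With a stop-date check:** the same, but not if a recorded stop date precedes the reference first dose. The dates below are illustrative.

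1. First dose 20 March; onset in March, day unknown; stopped 12 March. As written: TEAE. With the check: non-emergent. SAP 5.8: non-emergent.
2. The same patient, with only the onset year known; stopped 12 March. As written: TEAE. With the check: non-emergent.
3. Placebo patient, first casimersen dose 18 August; onset in August, day unknown; stopped 10 August. Tested against the casimersen start, the onset rule is met; with the check it is not. SAP 5.1 already gives the right placement: the stop date puts the event in the double-blind period, so it is excluded from the Casimersen Period.

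A known onset month or year earlier than that of the first dose is non-emergent under the rule as written, so those events are unaffected.

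**How often would a pre-dose onset pass the rule?** Assume onset uniform over the pre-dose window and Day 1 uniform over a 366-day year. For a 28-day window:

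- Day missing: a first dose on day d of a month leaves min(d − 1, 28) window days in that month. Summed over d, this is 462 for a 31-day month, 434 for a 30-day month and 406 for a 29-day February. Share = (7 × 462 + 4 × 434 + 406) / (366 × 28) = 5,376 / 10,248 = 52%.
- Day and month missing: (406 + 337 × 28) / 10,248 = 9,842 / 10,248 = 96%.

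For a 14-day window the shares are 75% and 98%. These are shares of pre-dose onsets with a partial date. They are not shares of events known to have ended before dosing, which are a subset, and they do not say how many partial dates there will be. Among events with a known pre-dose stop date, the check brings the share to 0%.

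**Effect of one misclassified patient in the double-blind tables.** Casimersen: 1/8 = 12.5 points. Placebo: 1/4 = 25 points.

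**The case against.** The strongest reply is that the rule is deliberately conservative. SAP 5.2.4 takes the same line, counting a missing relationship as related and a missing severity as severe. Original incomplete dates and all AEs are listed, so any over-count can be seen. The safety analysis is descriptive, and no test or threshold depends on it. The case is also rare. It needs an AE inside a Screening window of about 4 weeks, a partial onset date, a stop date good enough to show that it ended before dosing, and a shared calendar month or year. The protocol asks for onset date and time, 100% source data verification and queries on missing data, and it treats abnormalities present at Screening as medical history unless they recur or worsen.

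The argument on rarity stands and makes this a minor point. The argument on conservatism stands only where the timing is unknown. Where the stop date shows that the event was over before dosing, there is no uncertainty to be conservative about. Nor is the error always on the cautious side: in a placebo patient it adds a placebo TEAE, which can narrow the comparison with placebo named in the primary objective.

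A reader might infer three stronger things that the documents do not support:

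- That an event which began and ended on placebo is counted as a casimersen TEAE, or in both columns. SAP 5.1 excludes placebo patients' double-blind events from the Casimersen Period, and passing the treatment-emergent test does not override that filter. The error would need programming that ignores SAP 5.1.
- That the rule pushes events towards casimersen. A Screening event is counted in the randomized group, whichever that is.
- That a year-only date lets in events from many months before the first dose. AEs are recorded only from consent, so the pre-dose reach is the Screening period.

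**Conclusion.** The point holds in a narrow form and is minor. For an AE that began and resolved in Screening, whose partial onset date shares the month or year of the first dose, SAP 5.2.3 gives a result that contradicts SAP 5.8, although the stop date that would settle it is collected. One such patient shifts a double-blind incidence by 12.5 points (casimersen) or 25 points (placebo). Those are simply 1/n at the planned group sizes and say nothing about likelihood. The number of affected AEs is not given and is probably very small. The 52% and 96% shares rest on the uniform-onset and uniform-start assumptions.

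For patients who roll over from placebo, what remains is a matter of wording: SAP 5.2.3 does not name the reference dose for each analysis period, and it should be aligned with SAP 5.1.

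**What to change.** Add an exception to the AE bullet of SAP 5.2.3, modelled on the medication bullet: *unless the available stop date shows that the event ended before the first dose relevant to that analysis period (first study drug dose for the Double-Blind Period; first casimersen dose for the Casimersen Period)*. Keep the treatment-emergent default when the stop date is missing or does not settle the timing. Naming the reference dose also brings the bullet into line with SAP 5.1.

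The cost is one clause in the SAP and one condition in the AE dataset program. Onset and resolution dates are both already collected.

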### 5.2.4. Imputation of Relationship or Severity for Adverse Events

In the summary of AEs, events with missing relationship or severity will be presented as "Related" or "Severe," respectively. However, missing values will be presented in the data listings as missing.

### 5.3. Analysis Sets

Four analysis sets will be utilized with the definitions as appropriate.

**Safety Set:** For the double-blind period, the safety set will include all randomized patients who receive at least 1 dose of study drug (casimersen or placebo). For the combined double-blind and open-label period, the safety set will include all randomized patients who receive at least 1 dose of study drug (casimersen or placebo).

**Efficacy Set:** All randomized patients who received at least 1 dose of study drug (casimersen or placebo) and have at least 1 post-baseline functional assessment.

**Pharmacokinetic Set:** All randomized patients who receive the planned dose of study drug (casimersen or placebo) and for whom there are adequate PK samples from which to estimate PK parameters. The PK Set will be further described in a separate PK SAP.

CCI

### 5.4. Multiple Testing and Comparisons

No adjustment will be made for the testing of multiple endpoints.

### 5.5. Adjustment for Covariates

Not applicable.

### 5.6. Subgroups

Due to small sample size, no subgroup will be identified for this study.

### 5.7. Presentation Over Time

For endpoints that are collected serially, over time (eg, clinical laboratory tests), assessments/test values will be assigned to a specific time point (eg, study week) based upon the eCRF page on which the assessments/test values were reported. However, if a patient discontinues from the study early, then the EOS visit will be assigned to the nearest scheduled visit based on the duration on study provided that the EOS visit is within  $\pm 2$  weeks (14 days) of that scheduled visit.

Only for an efficacy endpoint, an unscheduled assessment may be used in the summary by time point if the unscheduled assessment was within 2 weeks of a missing scheduled assessment. Summaries of efficacy endpoints will include open-label period visits and results will be summarized by the nominal visit.

For safety endpoints, unscheduled assessments will not be included in the summary by time point.

## **5.8. Algorithm, Computation and Definition of Derived Variables**

### **Day 1**

Day 1 will be defined as the date of the first study drug administration (casimersen or placebo).

#### **Casimersen Day 1**

Casimersen Day 1 will be defined as the day of the first casimersen drug administration.

#### **Study Day**

Study day will be defined as Event Date - Day 1 + 1, if the Event Date is on or after Day 1; otherwise, as Event Date - Day 1, if the Event Date precedes Day 1.

#### **Casimersen Study Day**

Casimersen study day will be defined as Event Date - casimersen Day 1 + 1 if the Event Date is on or after casimersen Day 1; otherwise, as Event Date - casimersen Day 1, if the Event Date precedes casimersen Day 1.

#### **Duration of Study**

Duration of study will be calculated as the duration in weeks from Day 1 to the date of study completion/discontinuation as recorded on the END OF STUDY eCRF (if completed). The following formula will be used:

$$\text{Duration (weeks)} = (\text{Last visit date} - \text{Day 1 Date} + 1)/7$$

#### **Duration of Treatment**

Duration of casimersen treatment will be calculated as the duration in weeks from the date of first dose of casimersen to the date of the last casimersen administration as recorded on the STUDY DRUG ADMINISTRATION eCRF plus 6 days, (ie, last dose date - first dose date + 1 + 6)/7. Similarly, duration of casimersen treatment at dose  $\leq 20$  mg/kg will be calculated as the duration in weeks from the date of first dose of casimersen to the date of the last casimersen administration at dose level  $\leq 20$  mg/kg + 6 days. Duration of casimersen treatment at dose of 30 mg/kg will be calculated as the duration in weeks from the date of first dose of casimersen at 30 mg/kg to the date of the last casimersen administration at dose level of 30 mg/kg + 6 days. Duration of placebo treatment will be calculated as the duration in weeks from the date of first dose of placebo to the date of the last placebo administration + 6 days.

The duration in weeks calculated above will then be categorized to 1 of the following intervals: < 24, 24 to < 48, 48 to < 72, 72 to < 96, 96 to < 120, or  $\geq 120$ .

#### **Patient Years**

Patient Years will be calculated as the years from the first dose of casimersen to the date of the last casimersen administration as recorded on the STUDY DRUG ADMINISTRATION eCRF plus 6 days (ie, last dose date - first dose date + 1 + 6)/365.25. Similarly, patient years of casimersen treatment at dose  $\leq 20$  mg/kg will be calculated as the years from the date of first dose of casimersen to the date of the last casimersen administration at dose level  $\leq 20$  mg/kg + 6 days. Patient years of casimersen

treatment at dose of 30 mg/kg will be calculated as the years from the date of first dose of casimersen at 30 mg/kg to the date of the last casimersen administration at dose level of 30 mg/kg + 6 days. Patient years of placebo treatment will be calculated as the years from the date of first dose of placebo to the date of the last placebo administration + 6 days

[figure not shown]
### **Baseline**

Double-Blind Period (safety): Baseline will be defined as the last value prior to the first dose of study drug (casimersen or placebo) administration.

Casimersen Period (safety): Baseline will be defined as the last value prior to the first dose of casimersen administration.

Combined Double-Blind and Open-Label Period (efficacy): Baseline will be defined as the last value prior to the first dose of study drug (casimersen or placebo) administration.

CCI

### **Treatment-emergent Adverse Event**

An AE will be considered treatment-emergent if it started, worsened or became serious on or after the start of first infusion.

### **Treatment-related Adverse Event**

A treatment-related AE is any AE reported as definitely related, or probably/possibly related to study drug.

### **Treatment-emergent Laboratory Abnormality**

A treatment-emergent laboratory abnormality will be defined as any laboratory abnormality occurring or worsening after the initiation of study drug dosing and within 28 days of the last dose of study drug.

**Prior Medication**

A prior medication will be any medication taken and completed prior to the first dose of study.

**Concomitant Medication**

A concomitant medication will be any medication that is taken in the period starting with the initiation of the first dose of study drug dosing and ending 28 days after the last dose of study drug.

CCI

**Calculated Height**

Calculated height will be used based on the following formula:

$$\text{Height (cm)} = 4.605U + 1.308A + 28.003$$

where U is the length of the ulna measured by using an anthropometer or calipers, and A is the patient's age in years.

CCI

CCI

## 5.9. Programming Conventions

This section details general conventions to be used to produce tables, figures, and listings. Departures from these general conventions will be specified in appropriate sections.

- For continuous or quantitative variables, mean and median values will be formatted to 1 more decimal place(s) than the measured value on the eCRF. Standard deviation and standard error values will be formatted to 2 more decimal places than the measured value on the eCRF. Minimum and maximum values will be presented with the same number of decimal places as the measured value on the eCRF. Percentages will be presented with 1 decimal place.
- For categorical variables, the number and percentage of a category will be presented in the form XX (YY%), where the percentage is YY.
- Percentages of patients with laboratory toxicities will be based on nonmissing values unless stated otherwise.
- Study Day and Casimersen Day will appear in the data listings, as appropriate.
- Date variables will be formatted as DDMMYY YYYY for presentation. In the case of an unknown day, month, and/or year information, “UN”, “UNK”, or “UNKN” will be presented. For example, a date with a missing month and day will be presented as UNUNKYYYY.
- SAS® Version 9.4 or higher will be the statistical software package used for all analyses, unless otherwise specified.
- The Clinical Data Interchange Standards Consortium (CDISC) Analysis Data Model (ADaM) Implementation Guide (ADaMIG) V1.0 for preparing data sets will be used for this study.
- The CDISC Study Data Tabulation Model Implementation Guide (SDTMIG) V3.2 will be used for preparing data sets will be used for this study.
- Tables, figures, and listings will be presented in landscape orientation.
- Listings will be sorted by treatment sequence, patient, and date, unless otherwise specified.

